#### **4.2.1. Participants of Child-bearing Potential**

Human reproductive safety data are *not* available for DGAT2i + ACCi.

In the completed, nonclinical embryo-fetal developmental studies with DGAT2i alone and ACCi alone (and hence DGAT2i + ACCi in this study) findings have been noted, refer to [Section 2.3.1](#). Therefore, the **use of a highly effective method of contraception is required** by females of childbearing potential, refer to [Section 5.4.1](#) and [Appendix 10.4](#) for additional details.

The potential risk of exposure, via ejaculate, to DGAT2i + ACCi in a female sexual partner of childbearing potential of a male participant in this study is low. As such, use of barrier methods of contraception is *not* required/mandated in the male participants. The calculated safety margin is >100-fold between the estimated partner exposure due to seminal transfer and the NOAEL for serious manifestations of developmental toxicity in nonclinical studies. The safety margin of >100-fold is based on applying a 10-fold safety factor for interspecies extrapolation and a 10-fold safety factor for susceptible populations.

#### **4.2.2. Rationale for Banked Biospecimen Collections**

Banked Biospecimens will be collected and stored for further analyses which may, for example, provide greater understanding of the study intervention. Comparing the DNA, RNA, protein, and metabolite variation patterns of participants who respond well and those who respond poorly to treatment may help to better define the most appropriate group of participants in which to target a given treatment. Collecting biospecimens for exploratory pharmacogenomic/genomic/biomarker analyses and retaining them in the BBS make it possible to better understand the investigational product's mechanism of action and to seek explanations for differences in, for example, exposure, tolerability, safety, and/or efficacy not anticipated prior to the beginning of the study. Banked biospecimens retained in the BBS also can be used in research for NAFLD/NASH. Refer to [Section 8.8.1](#) for additional details.

Providing these biospecimens is a required study activity for study sites and participants, unless prohibited by local regulations or EC decision.

### 4.3. Justification for Dose

#### 4.3.1. Part 1

In Part 1, a range of doses of DGAT2i will be coadministered with fixed dose of ACCi (20 mg/day). Doses selected (refer to [Table 3](#)) were based on the observed effect on liver fat following 2 weeks of dosing with DGAT2i in Study C2541005, 6 weeks of dosing of DGAT2i alone, ACCi alone, and coadministration in Study C3711001, as well as 16 weeks of dosing with ACCi alone in Study C1171002.

In Study C3711001, administration of DGAT2i 300 mg BID and ACCi 15 mg BID alone and when coadministered over 6 weeks in participants with NAFLD, a placebo-adjusted LS mean reduction in liver fat of  $\geq 35\%$  was observed in all groups. In addition, on average, fasting serum triglyceride increases observed with ACCi alone were mitigated by coadministration with DGAT2i. In the current study, coadministration of DGAT2i + ACCi (at a ratio of 20:1) was selected as the highest dose; it contains the same DGAT2i dose assessed in Study C3711001 (DGAT2i 300 mg BID + ACCi 15 mg BID; at a ratio of 30:1) though a slightly lower ACCi dose (10 mg BID) is proposed in the current study acknowledging that while mitigation of ACCi-induced effect on fasting serum triglycerides with coadministration of DGAT2i was seen, this response had an upper 90% CI of an increase of 28% in placebo-adjusted change from baseline for DGAT2i + ACCi, in Study C3711001.

The lower doses of 50 mg/day and 200 mg/day of DGAT2i, administered BID (ie, 25 mg BID and 100 mg BID), in this study are proposed in order to assess the dose-response for mitigation of ACCi-induced elevations in fasting serum triglycerides, as well as to assess the effect of these coadministered doses on liver steatosis. Given that DGAT2i decreases PCSK9 with an ED50 of 7 mg BID and that PCSK9 is a marker of SREBP activity (mechanism postulated to be responsible for the DGAT2i-mediated mitigation of ACCi-induced elevations in fasting serum triglycerides), it is possible that doses significantly lower than 300 mg BID may mitigate ACCi-mediated lipid changes. Spacing of the DGAT2i doses by 3-4 fold allow for covering a 12-fold range of DGAT2i doses (ie, 50 to 600, mg/day).

In addition to a range of BID doses, a QD group is included where 300 mg DGAT2i will be coadministered with 20 mg ACCi. As 300 mg dose of DGAT2i represents the highest currently feasible QD dose, the purpose of this group is to assess the effect of a QD dosing regimen on hepatic steatosis as well as the potential to evaluate whether DGAT2i dose to mitigate ACCi-mediated elevations in fasting serum triglycerides can be administered QD. Depending on the observed profile with this QD dosing regimen in Part 1, additional dose ranging with QD doses may be considered in Part 2 of this study.

The DGAT2i and ACCi doses selected have been demonstrated to be safe and well-tolerated in previous clinical studies and are supported by the safety margins from the nonclinical, chronic toxicity studies completed in rats and monkeys for each of the agents alone and up to 13-week combination toxicity studies completed in monkeys. In the current study, the highest DGAT2i dose (300 mg BID) and ACCi dose (10 mg BID) proposed are 3 times (for DGAT2i) and 10 times (for ACCi) lower than the highest repeated dose evaluated for each

agent in previous clinical studies (refer to [Section 2.2.1](#)) as well as afford adequate safety margins compared to completed nonclinical chronic toxicity studies (refer to [Section 2.2.2](#)).

The overall selection of doses of DGAT2i and ACCi were also influenced by the aim to evaluate the study objectives using the tablet strengths available (ie, 25, 50, and 150 mg for DGAT2i; 10 mg and 20 mg for ACCi) as efficiently as possible. As proposed, the dose-range planned in Part 1 will necessitate each participant to self-administer 3 tablets/dose, twice daily, in order to maintain the double-blind, double-dummy design of the study. To aid compliance by the participants, study intervention will be packaged and dispensed as blister cards (not bottles) with each card permitting 7 days of dosing, refer to [Section 6.1](#).

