### 5.3. Randomization Criteria

A computer-generated randomization code using the method of random permuted blocks will be utilized to randomize participants equally balanced across the study interventions on Day 1/Visit 4 ***prior*** to the first dose of the double-blind, double-dummy study intervention provided participants satisfy ***all*** the following criteria:

1. Eligibility criteria outlined in [Section 5.1](#) and [Section 5.2](#);
2. A negative urine drug test for illicit drugs for sample collected at Baseline/Visit 3, as reported by Sponsor-identified central laboratory (with repeat assessment ***not*** permitted for this visit);
3. Fasting ( $\geq 8$  hours overnight, with water permitted) serum triglyceride result of  $\leq 400$  mg/dL (4.5 mmol/L), for sample collected at Baseline/Visit 3, as reported by Sponsor-identified central laboratory;
  - A single repeat assessment permitted using Sponsor-identified central laboratory, though results of this repeat, when done, must be available ahead of randomization;
4. Fasting ( $\geq 8$  hours overnight, with water permitted) plasma glucose result of  $\leq 270$  mg/dL (15 mmol/L), for sample collected at Baseline/Visit 3, as reported by Sponsor-identified central laboratory;
  - A single repeat assessment permitted using Sponsor-identified central laboratory, though results of this repeat, when done, must be available ahead of randomization, refer to [Appendix 10.10](#).
5. In females, a negative ***serum*** pregnancy test result for sample collected at Baseline/Visit 3, as reported by Sponsor-identified central laboratory;
  - ***Plus***, in females of childbearing potential, ***urine*** pregnancy test on Day 1/Visit 4, as reported on-site using supplies offered by Sponsor-identified central laboratory, must be negative for pregnancy, refer to [Section 8.2.6](#);
6. In those with hypertension, BP controlled via adjustment of concomitant medications for BP control during the Run-In period with seated BP on Day 1/Visit 4 of  $<160/100$  mmHg;
7. Compliance of  $\geq 90\%$  and  $\leq 110\%$  with ***doses*** of single-blind placebo administered (based on tablet count) from Baseline/Visit 3 to 1 day before Day 1/Visit 4, inclusive, refer to [Section 6.4](#);

8. Total score of <8 on the AUDIT questionnaire, as assessed on Day 1/Visit 4;

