**Table 4. Double-Blind, Double-Dummy Regimen in Part 1 of C3711005**

Regimen			# of DGAT2i Tablets (mg strength)				# of ACCi Tablets (mg strength)		
			placebo	25	50	150	placebo	10	20
A	Placebo, BID	AM	2	-	-	-	1	-	-
		PM	2	-	-	-	1	-	-
B	DGAT2i 25 mg BID + ACCi 10 mg BID	AM	1	1	-	-	-	1	-
		PM	1	1	-	-	-	1	-
C	DGAT2i 100 mg BID + ACCi 10 mg BID	AM	-	-	2	-	-	1	-
		PM	-	-	2	-	-	1	-
D	DGAT2i 300 mg QD + ACCi 20 mg QD	AM	-	-	-	2	-	-	1
		PM	2*	-	-	-	1*	-	-
E	DGAT2i 300 mg BID + ACCi 10 mg BID	AM	-	-	-	2	-	1	-
		PM	-	-	-	2	-	1	-

\* To maintain double-blind, double-dummy design across all groups, this group will receive placebo as evening dose.

**For Part 2, updated** dosing details will be offered via Investigational Product (IP) Manual for the site and separately for the participants via Dosing Diary Instructions once the data from Part 1 are reviewed and doses for Part 2 are identified.

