### **9.2. Sample Size Determination**

#### **9.2.1. Part 1**

The proposed sample size for this study is approximately 90 participants randomized (18 participants per group) to ensure at least 75 participants (15 participants per group) offer evaluable data. With a sample size of 15 completers per group and with natural log-transformed SD of 0.221 for liver fat (assessed via MRI-PDFF), a 25% placebo-adjusted liver fat decrease can be detected at a significance level of 5% 1-sided with a power >90%.

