#### **Analysis of percent change from baseline:**

The ANCOVA model will include the natural logarithmic transformed of relative change from baseline of the relevant endpoint as specified in [Section 6](#) as the dependent variable and will include treatment as a fixed effect and baseline as a covariate.

Missing values will not be imputed.

The adjusted geometric Least Squares Means (LSMeans) together with 80% confidence intervals and standard errors will be obtained for each treatment. Differences in adjusted geometric LSMeans between each treatment and placebo, together with 80% confidence intervals and standard errors, will also be obtained. All LSMeans and LSMeans differences (including CI's) will be back transformed to provide adjusted geometric LSMeans and ratios of adjusted geometric LSMeans. Then, percent change from baseline will be calculated as follows:

$$\text{Percent change} = 100 * (\text{RCBL} - 1)$$

where RCBL is either the adjusted geometric LSMeans estimate or the ratio of adjusted geometric means coming from the statistical model. The corresponding 80% CIs will be calculated as well.

Standard SAS output will be provided to support the main statistical summary table for the models.

Example SAS code is provided in Appendix 3.

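### Group D differs from every BID arm in both dosing frequency and DGAT2i daily dose, and no named output estimates QD against BID; a pre-specified supportive contrast would do so at little cost.

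*Protocol*

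**What the plan says.** **The role of Group D.** Protocol 4.3.1 states that "the purpose of this group is to assess the effect of a QD dosing regimen on hepatic steatosis". The group is also meant to show whether DGAT2i can mitigate the triglyceride rise when given once daily. Depending on its results, "additional dose ranging with QD doses may be considered in Part 2 of this study". Protocol 2.1 includes, in the purpose of the study, whether the effects persist with once-daily dosing of both agents. Protocol 9.5.1 and SAP 7.2 say the Part 1 interim is to enable the choice of dose(s) and regimen(s) for Part 2.

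**The arms.** Protocol Table 4 lists D as "DGAT2i 300 mg QD + ACCi 20 mg QD", with placebo in the evening. B, C and E take DGAT2i 25, 100 and 300 mg BID, each with ACCi 10 mg BID. Allocation is equal across the five arms.

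**The comparisons.** For the ANCOVA, SAP 5.2.4 says: "Differences in adjusted geometric LSMeans between each treatment and placebo, together with 80% confidence intervals and standard errors, will also be obtained". The outputs in SAP 6.1.1 and 6.2.1 likewise name each active treatment against placebo. The MMRM text in SAP 5.2.5 is wider and refers to comparing treatments at each week. The example code in SAP Appendix 3 requests differences without fixing a control level. Protocol 9.1.2 plans no hypothesis tests, and SAP 5.1 marks decision rules as not applicable.

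**The concern.** Two things change together between D and any BID arm: dosing frequency and DGAT2i total daily dose. A comparison with placebo shows whether the once-daily regimen has an effect. It does not show what, if anything, once-daily dosing gives up or gains relative to BID at the same daily dose.

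The display order adds to the difficulty. SAP Section 5 sorts arms by DGAT2i:ACCi daily-dose ratio, so D (15:1) will sit between C (10:1) and E (30:1), as if it were another point on the BID dose-response. If D matches or beats E, or falls clearly below C, the reading is fairly easy. If D lies between them, which is the likely place if frequency does not matter, the eye cannot separate dose from frequency. The regimen choice for Part 2 would then rest on informal interpolation made after unblinding.

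**Working it through.** **Inputs**
- SD 0.221 (log scale) and 15 per arm, from Protocol 9.2.1: "With a sample size of 15 completers per group and with natural log-transformed SD of 0.221 for liver fat".
- DGAT2i daily doses from Table 4: B 50, C 200, D 300, E 600 mg. ACCi is 20 mg/day in each.
- 80% confidence intervals, from SAP 5.2.4.
- Residual df 75 − 6 = 69 (five arms plus baseline); t(0.90) ≈ 1.294. Baseline imbalance is ignored.

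**Plan's own figure.** Pairwise SE = 0.221 × √(2/15) = 0.0807. A 25% decrease is ln 0.75 = −0.288. One-sided 5% power = Φ(0.288/0.0807 − 1.645) ≈ 97% (noncentral t: 96.7% to 97.0%). The stated power above 90% is reproduced.

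**The contrast.** Interpolate the BID response at 300 mg/day on log dose.
- Weight on E: ln(300/200)/ln(600/200) = 0.369. Weight on C: 0.631.
- Contrast: D − (0.631 C + 0.369 E), which equals 0.631(D−C) + 0.369(D−E).
- Variance factor: 1 + 0.631² + 0.369² = 1.534, against 2 for a pairwise difference.

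| Quantity (liver fat) | Contrast | Pairwise |
|---|---|---|
| SE | 0.221 × √(1.534/15) = 0.0707 | 0.0807 |
| 80% half-width, log scale | 0.0915 | 0.1044 |
| 80% limits around no difference | −8.7% to +9.6% | −9.9% to +11.0% |

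The SE ratio is √(1.534/2) = 0.876. The documents give no triglyceride SD, so for that endpoint only this ratio carries over.

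**Sensitivity to the weights.** A log-linear fit through B, C and E gives D − (0.125 B + 0.349 C + 0.526 E): variance factor 1.414, SE 0.0679. Linear-dose weights on C and E (0.75, 0.25) give SE 0.0727.

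**Interpolation error.** Suppose frequency has no effect.
- Emax curves (assumed ED50 14 to 1000 mg/day, maximum effect up to 0.4 log units): the C/E contrast is off by at most about 0.005 and the B/C/E version by about 0.012. Dose alone shifts D−C by up to 0.04 and D−E by up to 0.07.
- Steep Hill curves (assumed exponent 4, same maximum): the C/E contrast can be off by up to 0.06, nearly one SE.

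If the BID response is monotone from 200 to 600 mg/day, the true D−C and D−E bracket the true QD-versus-BID difference whatever the shape. Their estimates still carry sampling error.

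**What it can rule out.** The documents give no margin. With true equality, no interpolation bias and assumed margins, the chance that the 80% interval excludes a liver-fat ratio this much higher is Φ(ln m/0.0707 − 1.282): 53% for 10%, 76% for 15%, 90% for 20%. With the pairwise SE it is 46%, 67% and 84%.

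**After Part 2 pooling.** The precision gain needs roughly equal arms. With C still at 15, D−E has the smaller variance once E exceeds about 32. D versus pooled placebo does so once placebo exceeds about 28.

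**The case against.** The stated objectives compare doses with placebo, and no passage undertakes to show that QD matches BID at equal daily dose. D against placebo does address whether a once-daily regimen works. That stands, and it is why this is an addition to the plan and not a correction of its primary analysis.

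A reader might infer that the plan cannot say anything about QD against BID. The documents do not support that:
- The MMRM text and the unrestricted difference option in Appendix 3 would already produce D−C and D−E.
- PK/PD modelling is scheduled at about 50% and 100% of Part 1, feeds the interim, and could separate dose from frequency. Against that, Protocol 9.4.4 and SAP 6.3.9 make exposure-response modelling conditional and report it outside the main study report, and no QD-versus-BID estimate is specified.
- Part 2 may run both regimens, and its BID range (50 to 600 mg/day, Protocol 4.3.2) includes 300 mg/day. But Part 2 is optional, and the Part 1 data are used before it.
- Protocol 9.5 allows decision criteria to sit in a separate interim SAP, which is not available here.

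A reader might also infer that the contrast settles the question. It does not. It depends on interpolation, has no margin, and measures once-daily dosing of both drugs jointly, because ACCi also moves from BID to QD in D.

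**Conclusion.** The point holds as a cheap improvement. D differs from every BID arm in frequency and in DGAT2i daily dose, the named outputs compare it only with placebo, and no pre-specified estimate separates the two, although the regimen is one of the things Part 1 is meant to inform.

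The interpolated contrast supplies that estimate with an SE about 12% below a pairwise difference for liver fat. This rests on SD 0.221, 15 evaluable in each arm, and a BID response linear in log dose between 200 and 600 mg/day. The precision advantage applies to Part 1 and may not survive unequal pooling with Part 2. An 80% interval of roughly ±9% is an estimate; it would not demonstrate that QD works as well as BID.

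**What to change.** In SAP 6.1.1 (Week 6 MRI-PDFF, ANCOVA) and 6.2.1 (Week 6 triglycerides, MMRM), and in the Part 1 interim outputs, pre-specify as supportive:

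1. The log-scale contrast D − (0.631 C + 0.369 E), back-transformed, with 80% CI. Label it as the estimated effect of giving both drugs QD versus BID at DGAT2i 300 mg/day, assuming response linear in log dose from 200 to 600 mg/day.
2. D−C and D−E beside it, described as bounds if the BID response is monotone.
3. A sensitivity version fitted through B, C and E.
4. A sentence saying that no margin is set and that the result is not a demonstration of equivalence or non-inferiority.

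Before programming, reconcile the confidence level: the SAP text says 80%, while the Appendix 3 code sets alpha = 0.1, which gives 90% limits.

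The cost is one ESTIMATE statement per model for the main contrast, plus the sensitivity version, with no new data and no change to arms or doses. The weights should be fixed before unblinding, since weights chosen afterwards would be less credible. The downside is reliance on interpolation, which a steep dose-response could bias by nearly one SE.

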#### **4.3.2. Optional Part 2**

The planned dose range for DGAT2i + ACCi (both BID and QD) in Part 1 are envisioned to permit selection of dose(s) to be evaluated in Part 2.

Based on observed data in Part 1 (refer to [Section 9.5](#)), doses and/or dosing regimen selected in Part 2 will be in accordance with the following considerations:

- *Total daily doses* of DGAT2i, administered QD, will range from 25 mg (lowest) to 300 mg (highest);
- *Total daily doses* of DGAT2i, administered BID, will range from 50 mg (lowest) to 600 mg (highest);
- With DGAT2i doses projected to be sufficiently separated based on plasma exposure;
- Coadministered with ACCi dose of 10 mg/day *or* 20 mg/day with frequency mirroring DGAT2i dosing regimen – BID or QD;
- DGAT2i + ACCi dose(s) evaluated in Part 1 may be repeated to permit better characterization of effectiveness of DGAT2i to mitigate ACCi-induced elevation in fasting serum triglycerides;
- And each dose will be limited to  $\leq 4$  tablets (ie, up to 8 tablets per day) with drug packaged and dispensed as blister cards (not bottles) with each card permitting 7 days of dosing.

While data from Part 1 (via an interim analysis) will be used to guide dose groups evaluated in Part 2, data for any dose groups repeated in Part 1 and Part 2 (at a minimum placebo), will be pooled for purposes of reporting in the clinical study report.

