**Figure 2. Study Design for Part 1 and *Optional* Part 2**

Approximately 90 participants (18 per group) with Sponsor-defined presumed NASH will be randomly assigned to the study intervention to ensure approximately 75 evaluable participants (15 per group) offer evaluable data.

#### 4.1.2. Optional Part 2

Part 2 may be initiated after *unblinded* review of the data from Part 1 by selected members of the Sponsors' study team (the investigators/site staff as well as site-facing study team members will remain blinded), refer to [Section 9.5](#). This interim analysis will include review of primary endpoint data (effect on hepatic steatosis as assessed via MRI-PDFF) as well as overall safety/tolerability including degree of mitigation of ACCi-induced effect on fasting serum triglycerides achieved across the range of DGAT2i:ACCi dose ratios evaluated. Guided by these data, Part 2 may enroll up to 5 dose groups (including placebo) with intent to evaluate additional permutations of doses of both DGAT2i and ACCi administered BID or QD. However, the doses of DGAT2i in Part 2 will not exceed 300 mg BID or 300 mg QD and the dose(s) of ACCi will not exceed 20 mg/day (administered BID or QD to mirror dosing of DGAT2i). A maximum of 4 active doses (plus placebo) will be evaluated in Part 2; furthermore, the total number of participants will not exceed 90 (with no more than approximately 27 participants per each *active* dose).

Following aspects are envisioned to remain identical between Part 1 and *optional* Part 2:

- Eligibility (refer to [Section 5.1](#) and [Section 5.2](#)) and randomization (refer to [Section 5.3](#)) criteria;
- Schedule of activities including assessment of standard safety/tolerability (via vitals, 12-lead ECG, laboratory tests), refer to SoA – [Table 1](#) and SoA - [Table 2](#);
- Overall study design including duration of dosing, refer to [Figure 2](#).

In order to enable accumulation of safety experience in the clinical program, minimize potential carry over effect, as well as control selection bias, participants randomized and dosed double-blind, double-dummy study intervention in Part 1 of this study are not eligible for Part 2.

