### **6.3. Measures to Minimize Bias: Randomization and Blinding**

#### **6.3.1. Allocation to Study Intervention**

##### **6.3.1.1. Part 1**

Approximately 90 participants will be randomized in a balanced ratio to receive either double-blind, double-dummy placebo, or 1 of 4 doses of DGAT2i + ACCi (with 3 entailing BID dosing of DGAT2i + ACCi *and* 1 dose-level of QD dosing but with blind maintained via dosing of placebo as the 2nd dose each day). A computer-generated randomization code using the method of random permuted blocks will be utilized to assign participants to any 1 of the 5 dosing groups on Day 1/Visit 4.

Allocation of participants to treatment groups will proceed through the use of an IRT system (IWR). The site personnel (study coordinator or specified designee) will be required to enter or select information including but not limited to the user's ID and password, the protocol number, and the unique 8-digit participant number. The site personnel will then be provided with a treatment assignment, randomization number, and DU or container number(s) from the IRT system. The IRT system will provide a confirmation report containing the participant number, randomization number, and DU or container number(s) assigned. The confirmation report must be stored in the site's files.

The investigational product will be dispensed at the study visits summarized in the SoA - [Table 1](#); returned study intervention **should not** be redispensed to the participants.

The study specific IRT reference manual and IP manual will provide the contact information and further details on the use of the IRT system.

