## 5. GENERAL METHODOLOGY AND CONVENTIONS

Data from Parts 1 and 2 will be pooled for purposes of summarizing/analyzing end-of-study results and will be reported from placebo followed by ascending order of the DGAT2i to ACCi total daily dose (TDD) ratio (mg:mg).

In case the same co-administration ratio for BID and QD dosing regimen is evaluated, data will be reported 1st for BID and then QD while still in the ascending order for DGAT2i to ACCi TDD ratio (mg:mg).

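### If an active Part 1 dose is repeated in Part 2 because its Part 1 results looked good, the only planned estimate includes the data that selected it and can overstate its effect

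*Protocol*

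**What the plan says.** Protocol 4.1.2 and 9.5 let selected sponsor staff review Part 1 unblinded, covering MRI-PDFF, safety and the degree of triglyceride mitigation. That review decides whether Part 2 runs and at which doses. Protocol 4.3.2 allows a Part 1 combination to be given again: "dose(s) evaluated in Part 1 may be repeated to permit better characterization of effectiveness of DGAT2i to mitigate" the triglyceride rise. The same section states that "data for any dose groups repeated in Part 1 and Part 2 (at a minimum placebo), will be pooled for purposes of reporting" in the study report, and Protocol 9.3 repeats this. SAP 5 is broader: "Data from Parts 1 and 2 will be pooled for purposes of summarizing/analyzing end-of-study results".

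SAP 5.2.4, 5.2.5, 6.1.1 and 6.2.1 specify one contrast with placebo per treatment (per week for triglycerides), with ordinary 80% intervals and p-values. The models contain treatment and baseline, plus week for the repeated measures, but no term for Part. No Part 2-only estimate, selection adjustment or sensitivity analysis appears, and SAP 6.4 plans no subset analyses.

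Protocol 9.5 says the decision criteria will be approved in an interim SAP or the final SAP before the interim analysis. In the SAP supplied, 5.1 marks decision rules as not applicable and 7.2 gives no rule for choosing doses. Protocol 9.1.2 plans no formal hypothesis tests.

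**The concern.** A dose that looks good in Part 1 does so partly because it is good and partly by chance. If looking good is the reason it is repeated, the chance part is carried into the pooled mean and only diluted by Part 2. The ordinary interval takes no account of this. The issue is separate from any drift between Parts, and a Part term in the model would not remove it.

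The stated purpose of repeating a dose is to characterise triglyceride mitigation better, and triglycerides are among the data reviewed for selection. Selection and estimation can therefore rest on the same endpoint. Protocol 9.5 says the interim results may inform planning of future trials, so an optimistic figure for a repeated dose could be carried into that planning.

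**Working it through.** **1. The plan's own figure.** Protocol 9.2.1 gives "approximately 90 participants randomized (18 participants per group) to ensure at least 75 participants (15 participants per group) offer evaluable data", an SD of 0.221 on the log scale, a 25% placebo-adjusted decrease and one-sided 5%. SE = 0.221 × √(2/15) = 0.0807; -ln 0.75 = 0.2877; 0.2877/0.0807 = 3.565; 3.565 - 1.645 = 1.920; power = 97.3%. The stated power above 90% is reproduced. It concerns Part 1 liver fat only and says nothing about a pooled, selected dose.

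**2. Inputs.** From the documents: 15 evaluable per arm, "1 of 4 doses of DGAT2i + ACCi" plus placebo in Part 1, at most 90 participants and about 27 per active dose in Part 2, placebo possibly reduced, 80% intervals (10% per side). Assumed, because the documents give no value: triglyceride log SD 0.3-0.5, 18-27 analysed on the repeated dose, 9 Part 2 placebo, known SD, no drift between Parts.

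**3. Bias when the best of four equal doses is repeated.** The most favourable of four standard normal values averages 1.029. The Part 1 arm SE is SD/√15, and Part 1 has weight 15/(15 + n2) in the pooled mean.
- SD 0.3, n2 = 27: (15/42) × 1.029 × 0.3/√15 = 0.357 × 1.029 × 0.0775 = 0.028.
- SD 0.5, n2 = 18: (15/33) × 1.029 × 0.5/√15 = 0.455 × 1.029 × 0.129 = 0.060.

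The placebo-adjusted triglyceride ratio is thus about 3% to 6% too low.

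**4. Simulation of other rules.** There were 400,000 two-part trials per case, with 20 active in Part 2 (18-27 in the first row). Effects are log triglyceride rises over placebo, lowest to highest dose. The last column is the share of trials whose upper 80% limit falls below the true effect.

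| Dose repeated | True effects | Bias (log) | Error (nominal 10%) |
|---|---|---|---|
| Best of four | equal | -0.028 to -0.061 | 17-19% |
| Best of four | 0.20/0.15/0.05/0 | -0.021 to -0.046 | 15-17% |
| Best of four | 0.5/0.3/0.15/0 | -0.008 to -0.027 | 12-14% |
| Lowest dose with observed rise ≤0.10 | either unequal pattern, or all 0.10 | -0.03 to -0.07 | 16-19% |
| Lowest dose with observed rise ≤0.10 | all 0 | -0.01 to -0.03 | 11-12% |
| Second best | equal or either unequal pattern | 0 to -0.02 | 10-11% |
| Closest to 0.10 | equal or either unequal pattern | -0.01 to +0.03 | 4-10% |
| Worst-looking | equal | +0.03 to +0.06 | about 4% |

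With equal effects the error does not depend on the SD. For liver fat at the protocol's 0.221, best of four with 15-22 active and 8 placebo in Part 2 gives 18.0-19.7% and a bias of 0.024-0.029 log units.

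**5. Two-sided coverage.** For equal effects, best of four and 20 active, the misses are 18.6% on one side and 3.6% on the other, so coverage is 100 - 22.2 = about 78% against 80%.

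**6. Part 2-only contrast with Part 2 placebo.** Bias is nil and the error is 10% under every rule tried. SE relative to pooled: √(1/18 + 1/9)/√(1/33 + 1/24) = 0.408/0.268 = 1.52 with 18 active, and √(1/27 + 1/9)/√(1/42 + 1/24) = 0.385/0.256 = 1.50 with 27. Root mean squared error (equal effects, best of four, SD 0.4, 20 active) is 0.111 pooled, bias included, against 0.160 Part 2-only, a ratio of about 1.45. In other cases the ratio reaches about 1.8.

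**The case against.** The strongest reply is that the problem is conditional. Part 2 is optional, repeating an active dose is optional, and only placebo is certain to be pooled. The study looks for the lowest dose that mitigates the triglyceride rise, not the largest observed effect. A dose may be repeated because it was borderline or imprecise, and then the bias is nil or reversed. Selection also draws on liver fat, safety, exposure separation and PK/PD modelling, which weakens its link to one arm mean. Selecting on an uncorrelated endpoint leaves the error at 10%. Equal effects fit poorly with a 12-fold dose range. A separate interim SAP, not among the documents supplied, may state the rule.

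Most of this stands, and it rules out reading 15-19% as a property of the plan or saying that a repeated dose's effect will be overstated. It does not remove the point. A lowest-passing-dose rule, closer to the study aim, still gives 16-19% when some doses truly miss the threshold or all sit on it, and nothing in the supplied documents excludes such a rule.

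A reader might also infer inflated type I error. No formal tests are planned, so what is at issue is coverage, and the two-sided loss is small. The 10% benchmark follows the SAP text; the example code in SAP Appendix 3 uses alpha = 0.1, which makes it 5% per side. Finally, one might want the Part 2-only figure to replace the pooled one. Step 6 argues against that: the pooled estimate has the smaller total error even with its bias.

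**Conclusion.** The point holds as a conditional one. If an active dose is repeated because its Part 1 results looked favourable, the plan reports only an estimate that contains the selecting data. Under the assumptions in step 2, the bias is about -0.02 to -0.07 log units and the favourable-side error of the 80% limit about 15-19% instead of 10%. This applies to the best of four similar doses, or to the lowest dose passing a threshold that not all doses truly clear. The error is about 12-14% for the best of well-separated doses, 11-12% if all doses clear the threshold, and about 4-11% if a second-best, borderline or poor-looking dose is repeated. The triglyceride SD, the Part 2 placebo size and the selection rule are not in the documents, so these are ranges and not predictions. Nor do the documents support inferring that the dose taken into later development will be the repeated one. This is a cheap improvement to an exploratory analysis, not a flaw that invalidates it.

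**What to change.** In SAP 5, 6.1.1 and 6.2.1, keep the pooled estimate. For every active dose repeated in Part 2, add a sensitivity row giving the Part 2-only randomised contrast with concurrent Part 2 placebo and its 80% interval. Footnote the pooled figure as including the data used to select the dose. The concurrent placebo matters: if the choice used differences from Part 1 placebo, a comparison of Part 2 active with pooled placebo would still carry part of the selection.

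The cost is SAP wording and one table row per repeated dose, with no new data. If no active dose is repeated, nothing changes. The downside is that the added interval is about 1.5 times as wide with 9 Part 2 placebo participants, so it should be labelled as supplementing the pooled estimate, not replacing it.
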